TITLE: Intervention for Teens with ADHD and Substance Use

- PROTOCOL NO.: DA034731
- **SPONSOR:** National Institute on Drug Abuse
- **INVESTIGATOR:** [name], Ph.D.
- **SITE(S):** Florida International University
- **DATE:** June 4, 2019

ABSTRACT

Individuals with ADHD are at markedly high risk for increased substance use and Substance Use Disorder (SUD; Barkley et al., 2004; Charach et al, 2011; Derefinko & Pelham, in press; Lee et al., 2011; Molina & Pelham, 2003; Sibley et al., 2011). They have high rates of substance use across a wide range of substances, including illicit drugs, alcohol, and cigarettes (Arias et al., 2008; Molina & Pelham, 2003; Szobot et al., 2007), and are at risk for early onset of substance use behaviors and disorders (Arias et al., 2008; Milberger et al., 1997; Molina & Pelham, 2003). Importantly, these substance use problems do not abate over time; among individuals with adult ADHD, rates of substance use disorders approach 40% (Kalbag & Levin, 2005; Biederman et al., 1995), suggesting the need for early intervention. However, treatment of ADHD and substance use concurrently presents a number of problems for clinicians, including poor treatment adherence, lack of treatment progress, and impaired achievement of treatment goals, (Carroll & Rounsaville, 1993; Levin et al., 2004; Wise et al., 2001). Given these barriers, it is clear that future prevention and intervention development should follow the quidelines provided by the current literature on both ADHD and substance use treatment. Several psychosocial interventions for teens with SUD are well-established (Waldron & Turner, 2008; Winters & Leitten, 2007). However, typical studies that have examined efficacy of substance use interventions have conducted only secondary analyses to see if comorbid psychiatric diagnoses moderate outcome. There have been no controlled evaluations of how comorbid ADHD affects the efficacy of early intervention for early substance use. Given the strong evidence for the negative trajectory for individuals with co-occurring ADHD and substance use initiation, our goal is to conduct a controlled examination of a brief. early intervention for substance use (BEI; Teen Intervene, Winters & Leitten, 2007) modified for adolescents with ADHD by using the evidence from both treatment literatures. Importantly, this intervention will address individuals who are at risk for problems with substance use, but do not yet meet criteria for severe SUD. Although brief interventions have been found to be effective in other populations, their efficacy in an ADHD population with emerging substance use remains uninvestigated. We expect BEI to be effective for some but not all ADHD teens, with lower rates of response than have been obtained with nonADHD populations. To better understand why some adolescents with ADHD and elevated risk for substance use problems respond to BEI and others do not, we investigate the contributions of several cognitive, proximal and situational factors to treatment response. Finally, we will randomize non-responders to the BEI to three secondary treatment conditions (monitor only, parent training/adolescent cognitive behavioral therapy, and medication plus parent training/adolescent cognitive behavioral therapy) to determine the relative efficacy of these more intensive interventions for insufficient responders to brief treatment.

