Adolescents will be evaluated for treatment non-response to the BEI at 6, 9, 12, 15, and 18 months posttreatment. Non-response is defined as non-normative use of alcohol, marijuana, or other drugs in the past 90 days. Alcohol and marijuana are the outcomes of interest in this study; however, non-normative use of any psychoactive substance will be considered non-response. Alcohol use norms by age are presented in Table 4 and any marijuana use in adolescence is considered non-normative (NHSDAH, 2007). Tobacco and caffeine products are excluded from consideration. For alcohol, marijuana, and other drugs, frequency and quantity of substance use will be collected for the past 90-days using the Substance Use Questionnaire (SUQ). Adolescents who do not demonstrate a response to the BEI at the 6, 9, 12, 15, or 18 month assessment (i.e., use substances at non-normative levels) will be randomized to either (1) No Additional Treatment Monitoring Group, (2) Parent Training/Adolescent CBT (PT/ACBT; e.g., 12 weeks of parent training and adolescent CBT) (3) PT/ACBT plus concurrent stimulant medication (PT/ACBT+MED). Adolescents who demonstrate immediate initial response will be released from treatment and assigned to a monitoring condition in which they are reassessed at 9, 12, 15, and 18 months. Any adolescent who demonstrates non-normative use at any of the follow-up assessments as defined above will be immediately eligible for randomization to further treatment (as detailed above). Adolescents and parents will complete an assessment battery at the randomization point as outlined in Table 5 unless randomization occurs immediately following the 6 or 12 month assessment (in which case the measures will not need to be repeated).

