It is important for adolescents to be able to participate in research and substance use problems prevention programs without being required to disclose substance use to parents. Without this guarantee of confidentiality, adolescents have a disincentive to participate in this study and to provide honest disclosure of substance use. Therefore, participants will not be informed that the specific reason for randomization is the presence of adolescent substance use. Rather, parents and youth will be provided with a more general description of the reason for randomization: youth who demonstrate a lack of progress toward the treatment goals of the initial brief intervention will be assigned to the second arm of the study for randomization. Further, parents and adolescents will be informed of the purpose of interventions included in the secondary arm of the study (i.e., preventing the escalation of substance use problems among adolescents) and will provide consent/assent to participate in the treatment.

Based on prior research with Teen Intervene, and correcting for the likelihood that the ADHD sample in the proposed study represents a more intervention resistant group than was the case in the Winters et al. studies, we conservatively expect that the **6**-month non-response rate will be over 50%. Thereafter, adolescents who demonstrate non-response post-BEI and are randomized will be assessed at post-treatment (6 months following randomization), and one year follow-up (12 months after post-treatment assessment).

Revised Protocol Version 06042019

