Age	Alcohol days per month						
12	0						
13	0						
14	0						
15	1						
16	2						
17	2						
18	3						

symptoms of either hyperactivity/impulsivity or inattention may still receive ADHD diagnoses for the purposes of this study when there is evidence of significant impairment. This decision is based on the finding that severity of impairment may be a better indicator than symptom counts of the presence of ADHD among adolescents (Sibley et al., 2012). Exclusionary criteria will include: (1) current substance use disorder meeting DSM-V criteria for the severe qualifier; (2) active medical conditions that could be worsened by stimulants (seizures, pregnancy, arrhythmias, hypertension, Tourette's Disorder, etc.) unless approved for participation by the treating physician; (3) a formal

diagnosis of Bipolar Disorder, schizophrenia, and/or other psychotic disorders (4) a formal diagnosis of autism spectrum disorder (ASD) with a severity level of 2 or 3 or significant intellectual or language impairment. Youth with a documented intolerance to amphetamine or methylphenidate will not be enrolled as this would eliminate the possibility for randomization to the medication arm of the study. Youth with a mood or anxiety disorder not

Revised Protocol Version 06042019

requiring psychotropic medication will be allowed to enroll as long as they do not need emergent treatment (mania, active suicidal ideation).

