Follow-up Assessment and Interventions. The schedule of assessment and interventions will depend upon participants' progress following the initial brief intervention. Participants meeting study criteria will participate in the activities as outlined below. Table 5 details the schedule of assessment for responders (i.e., teens engaging in no more than normative substance use following the brief intervention) and non-responders (i.e., teen engaging in more than normative substance use following the brief intervention). Participants who are initially identified as responders, may be subsequently identified as non-responders should there be evidence of non-normative use at any of the assessment points from 6 to 18 months. Once identified as a non-responder, participants are randomized to one of the three previously described treatment conditions. The post-treatment assessment point will occur 6 months after the start date for the treatment. The 1-year follow-up will occur 1 year after the post-treatment assessment.

Parents and teens will each receive \$25 in gift cards upon completing each assessment point with the exception of the 9, 15, and 18-month screens. For the 9-month, 15-month, and 18-month screens, each teen who completes the assessment will receive \$25 in gift cards. Teachers will receive a \$10 gift card each time they return completed measures.

Table 5. Assessment measures Study 1

Baseline Diagnostic Measures	All Participants				Responder	Non-Responders				
	Intake	6-Month	9- Month Screen	12- Month	15- Month Screen	18- Month Screen	24- Month	Random- ization Visit ¹	Post-Tx	1-Year Follow-Up
Telephone Screening	Р							-		
Diagnostic Interview Schedule for Children (DISC-IV; Shaffer et al., 2000)										
ADHD Module	Р									
ODD Module	P		-							
CD Module	Р							-		
Parent Report of Son/Daughter Substance Abuse (PRASU) Baseline Version	Ρ									
Parent Report of Son/Daughter Substance Abuse (PRASU) Past 3 month Version		Ρ		Ρ			Ρ	Ρ	Р	Ρ
Family Information Form	Р									
Clinical Intake Interview	Р									
Adolescent Diagnostic Interview - Baseline Version (ADI ITAS Baseline) Adolescent Diagnostic	A							-		
Interview - Past 3 Month Version (ADI ITAS Past 3 Month)		A		A			A	A	A	A
Wechsler Abbreviated Scale of Intelligence - 2nd Ed (WASI-II; Wechsler, 2011)										
Vocabulary	A									
Matrix Reasoning	A		-							
Wechsler Individual Achievement Test - 3rd Ed. (WIAT-3; Wechsler, 2002)										
Word Reading	А									

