Alcohol Use Questionnaire	P									
Cigarette Use Questionnaire (PALS)	Р									
Bidimensional Acculturation Scale	PA									
Treatment History Form	Р	Р	Р	Р	Р	Р	Р	Р	Р	Р
Readiness to Change Ruler (Miller)	Α	A		A				Α	A	Α
IGIC-R (Trucco) Note P=Parent A=Adolescent T	A									

Note. P=Parent. A=Adolescent. T=Teacher.

¹ These measures will only be completed by families who are randomized following the 9, 15, or 18-month screening point.

Interventions. The Brief Intervention will be a brief early intervention program based upon Teen Intervene, an early intervention designed by Winters (Winters & Leitten, 2007). Due to the known executive functioning

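### Severe SUD is an exclusion at entry but is not checked at second-stage randomization, so a teen who has progressed to it could be assigned to No Additional Treatment with no stated referral rule

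*Combined protocol and SAP*

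**What the plan says.** **Entry.** The Abstract describes the target group as "at risk for problems with substance use, but do not yet meet criteria for severe SUD". The Inclusion/Exclusion section turns this into a criterion, excluding "current substance use disorder meeting DSM-V criteria for the severe qualifier". Non-normative use, and SUD below the severe level, do not exclude a teen.

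**Second stage.** Research Design and Methods defines non-response to the brief early intervention (BEI) as non-normative use in the past 90 days, assessed at 6, 9, 12, 15 and 18 months after treatment. It then says: "Any adolescent who demonstrates non-normative use at any of the follow-up assessments as defined above will be immediately eligible for randomization to further treatment". Follow-up Assessment and Interventions repeats the rule: "Once identified as a non-responder, participants are randomized to one of the three previously described treatment conditions". The three conditions are No Additional Treatment Monitoring, PT/ACBT, and PT/ACBT plus stimulant medication. Assessments after randomization come at 6 months and 12 months after that.

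**What is measured.** Table 5 schedules the past-3-month ADI at the 6- and 12-month assessments and at a randomization visit. Its footnote says of that visit: "These measures will only be completed by families who are randomized following the 9, 15, or 18-month screening point".

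**What families are told.** To protect the teen's confidentiality, "participants will not be informed that the specific reason for randomization is the presence of adolescent substance use". They are told that progress toward the BEI goals has been insufficient, and that the second-stage interventions are meant to keep substance use problems from escalating. Consent and assent are sought for that stage.

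**The concern.** The second-stage rule has a floor, non-normative use, but no ceiling. Severity is screened at intake, yet randomization can come as late as 18 months after the BEI. The teens who reach it are, by definition, still using above the norm after treatment. Followed as written, the rule lets chance decide whether a minor who now meets the trial's own exclusion criterion receives any further study treatment.

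The protocol recognizes this kind of risk elsewhere. Among its reasons for having no control group at the first stage, Research Design and Methods cites unease about leaving at-risk adolescents untreated for one to two years. The 18 months of second-stage follow-up fall within that range. An untreated arm for non-responders in general may well be justified. The question is only whether a teen with severe SUD should be eligible for it.

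**Working it through.** The plan gives no rate of severe SUD at randomization, so there is no figure of its own to reproduce. The check compares the text and then gives a scale under stated assumptions.

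**Text comparison**

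| Point | What the plan provides |
|---|---|
| Intake | Severe SUD excluded (Inclusion/Exclusion) |
| Second-stage trigger | Non-normative use, no upper limit (Research Design and Methods; Follow-up Assessment and Interventions) |
| SUD information at randomization | ADI at 6 or 12 months, or at the randomization visit for those triggered at 9, 15 or 18 months |
| Decision tied to that ADI | None stated |
| Referral or rescue rule for severe SUD | None stated in Potential Risks or Confidentiality Assurances, which cover consent, withdrawal, emergencies, abuse and imminent serious harm |

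Every randomized teen should thus have an ADI at the point of randomization. The documents do not say whether the past-3-month version grades severity.

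**Scale (illustrative)**

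Inputs: 150 randomized teens (Aim 3 analysis); equal allocation, assumed because no ratio is given; severe-SUD rate p, assumed equal and independent across teens.

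- Untreated arm: 150 / 3 = 50.
- Expected severe cases in that arm: 50p.
- Chance of at least one there: 1 − (1 − p)^50.
- Teens not randomized under the fix: 150p.

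| p | 50p | Chance of at least one | 150p |
|---|---|---|---|
| 0.1% | 0.05 | 5% | 0.15 |
| 0.5% | 0.25 | 22% | 0.75 |
| 1% | 0.5 | 39% | 1.5 |
| 5% | 2.5 | 92% | 7.5 |

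The result depends almost wholly on p, which is not known.

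**Effect of the fix on power**

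The Power Analysis section uses an effect size of .40, 15% dropout and 150 teens for Aim 3, but does not say what the .40 is. Two readings were tried, at two-sided alpha .05 for the t-test and alpha .05 for the F-test, with N = 150 × (1 − p) × 0.85.

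| p | N | N per arm | Pairwise t-test, d = .40 | Three-arm ANOVA, f = .40 |
|---|---|---|---|---|
| 0 | 127.5 | 42.5 | 0.445 | 0.985 |
| 0.1% | 127.4 | 42.46 | 0.445 | 0.985 |
| 1% | 126.2 | 42.07 | 0.442 | 0.984 |
| 5% | 121.1 | 40.38 | 0.427 | 0.980 |

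Neither reading returns the section's .90. The table is used only for the change from the first row to the last: 0.018 on one reading and 0.005 on the other.

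**The case against.** **Stage 2 has its own population.** Aim 3 asks what to do given non-response to the BEI, and the entry criterion concerns current disorder at entry. A reader might infer that Aim 3 enrolls the wrong population, or that its analysis is invalid. The documents do not support that. Stage 2 is defined by non-response, some participants worsen after entry in any trial, and randomizing all non-responders answers the question as posed. This objection stands, and the point is one of safety only.

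**Families are not left in the dark.** A reader might infer from the confidentiality terms that parents have no reason to seek help. That goes too far. Parents are told of the lack of progress and the purpose of the second stage, join parts of three BEI sessions, and report on the teen's substance use themselves. Potential Risks says families need not take part in the assigned group and that withdrawing does not affect later clinical services at the center. Outside care is not barred, and the Treatment History Form is collected. These routes are real, but each relies on the family acting, and none tells a parent that this teen's disorder has become severe.

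**Material not seen.** The consent pages and the design figure were not available to this review, and referral language may be in the consent form. This stands as a limit. Such language would help after assignment, but the rule in the text would still randomize the teen.

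**Unknown frequency.** The assumed rates have no basis in the documents, and at three of the four the expected count in the arm is 0.5 or less. This also stands: the numbers show a range, not a likelihood.

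**Going further.** One could also ask for treatment to be offered to any teen found with severe SUD at the post-treatment assessment. That would mix later treatment into the one-year comparison. It is a debatable trade-off and is not proposed here.

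**Conclusion.** The gap is real in the text: severity limits entry but not second-stage randomization, and one of the three conditions gives no further study treatment over 18 months of follow-up. No referral or rescue rule for severe SUD appears in the text available. It should be closed because the possible harm falls on a minor and the information needed is largely scheduled already.

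The size is uncertain. With 150 teens, equal arms and assumed rates of 0.1% to 5%, the expected number of severe cases in the untreated arm runs from 0.05 to 2.5, and the chance of at least one from 5% to 92%. The documents do not show that any such case will occur. Confidence is medium, subject to what the consent form says. Nothing here bears on the validity of the Aim 3 analysis.

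**What to change.** Before second-stage randomization, review the past-3-month ADI from the 6- or 12-month assessment or the randomization visit, and apply the severe-SUD criterion again. If that version does not grade severity, add a DSM-5 criterion count. Complete the review before the assignment is drawn. A teen with current severe SUD is not randomized, is offered referral or PT/ACBT, and is counted and reported. Referral should be a real option, since nothing in the documents shows that PT/ACBT is sufficient for severe SUD. Keep the protocol's existing confidentiality approach: the parent hears of insufficient progress toward the BEI goals, and the second-stage consent says that some youth are offered care directly. First check whether the consent form already holds a referral provision.

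Costs:

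- One protocol and consent amendment with IRB review; no new visits.
- Aim 3 conclusions are limited to non-responders without severe SUD.
- At the assumed rates, 0.15 to 7.5 of 150 teens are not randomized. Power goes from 0.445 to no lower than 0.427, or from 0.985 to no lower than 0.980.
- If all accept PT/ACBT, the extra load is the third who would have had none: 50p courses of 12 sessions, or 0.6 (0.05 × 12) to 30 (2.5 × 12) sessions.
- A parent may infer use from a direct offer, and a teen who expects this may report less openly. The wording above reduces that risk but does not remove it.

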Aim 3: The third aim is to determine if, given nonresponse to the BEI, it is preferable to augment treatment with enhanced psychosocial intervention or multimodal treatment. As previously stated, we expect less than 50% of the sample to respond to the BEI, leaving at least 150 treatment-resistant adolescents to be randomized into one of the three treatment arms: (1) No treatment, (2) PT/ACBT, (3) PT/ACBT + MED. Using the general linear modeling techniques as implemented by SAS PROC GLM, we will examine differences between the treatment arms over post-treatment and one year follow-up measurement points with fixed effects of treatment arm. Analyzing each time period will address separate questions about the effect of intervention immediately post-treatment and at one-year follow-up. For these analyses, mixed linear models and/or GEE strategies will be used (Hedeker et al., 2006). Primary and secondary outcome measures will be evaluated separately (see Table 5). As our sample size permits, as a secondary analysis, we will also examine whether changes in the secondary outcomes listed above following treatment mediate response to treatment and substance use during the follow up phase.

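### The Aim 3 post-treatment visit is timed from randomisation in one section and from treatment start in another, and the monitoring arm has no treatment start date

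*Combined protocol and SAP*

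**What the plan says.** Two sections of the current text time the same visit for adolescents randomised after not responding to the BEI.

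- Research Design and Methods: these adolescents "will be assessed at post-treatment (6 months following randomization), and one year follow-up (12 months after post-treatment assessment").
- Follow-up Assessment and Interventions: "The post-treatment assessment point will occur 6 months after the start date for the treatment". It continues: "The 1-year follow-up will occur 1 year after the post-treatment assessment".

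The arms are named in Research Design and Methods, where the first is the "No Additional Treatment Monitoring Group". The Aim 3 analysis text lists them as ("1) No treatment, (2) PT/ACBT, (3) PT/ACBT + MED". Follow-up Assessment and Interventions also says that "participants are randomized to one of the three previously described treatment conditions", so it applies the word treatment to monitoring as well.

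On the outcome, Research Design and Methods says that "frequency and quantity of substance use will be collected for the past 90-days". That sentence concerns response to the BEI. Table 5 carries the past-3-month version of the same questionnaire, together with a urine screen, to the Post-Tx and 1-Year Follow-Up visits.

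**The concern.** Aim 3 is the trial's only randomised comparison, and its analysis contrasts the arms at exactly these two visits. A visit anchored on treatment start has no defined date in three situations:

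- **Monitoring arm.** Nothing is started, and no notional start date is given.
- **Teens who stay in the study but never start.** Potential Risks allows families to decline the assigned treatment. It does not say whether such teens are still assessed.
- **PT/ACBT+MED.** The start could be the first session or the first dose. Under Interventions, teens already on ADHD medication at randomisation see the study doctor before study medication begins.

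Staff would have to supply a date in each case. If they timed monitoring from randomisation and the treated arms from a later start, the arms would report substance use over different calendar stretches after randomisation. The Aim 3 text names fixed effects of arm and mixed models and/or GEE, but does not say how unequal elapsed time would be handled.

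**Working it through.** **1. The two rules side by side.**

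| | Research Design and Methods | Follow-up Assessment and Interventions |
|---|---|---|
| Post-treatment visit | 6 months from randomisation | 6 months from treatment start |
| One-year visit | 12 months after the post-treatment visit | 1 year after the post-treatment visit |
| Date exists for monitoring? | Yes | Not defined |
| Date exists for a teen who never starts? | Yes | Not defined |

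The rules coincide only at zero delay between randomisation and treatment start. The protocol neither states a zero delay nor limits it. There is no published figure to reproduce here, and no sample size or power figure depends on the point.

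**2. Size of the shift (illustration).** Inputs: 6 months = 182.6 days, one month = 30.44 days, recall window 90 days. Assumptions: treated arms follow the treatment-start rule, monitoring is timed from randomisation, and the delay d is 0, 4, 8 or 12 weeks. The documents give no value for d.

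- Shift of the window between treated arms and monitoring = d
- Recall days in common = 90 − d
- Treated-arm visit in months since randomisation = (182.6 + d) / 30.44
- One-year visit = that value + 12

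| Delay d (days) | Shift (days) | Days in common | Post-treatment visit (months) | One-year visit (months) |
|---|---|---|---|---|
| 0 | 0 | 90 | 6.0 | 18.0 |
| 28 | 28 | 62 | 6.9 | 18.9 |
| 56 | 56 | 34 | 7.8 | 19.8 |
| 84 | 84 | 6 | 8.8 | 20.8 |

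With randomisation as the anchor in all arms, the shift is zero at any delay.

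**3. What a randomisation anchor costs.** The recall window opens on day 182.6 − 90 = 92.6 after the anchor. For a course of L days that starts d days after randomisation, the recall days inside the course are max(0, min(d + L, 182.6) − max(d, 92.6)). The protocol gives the length only as an example ("PT/ACBT; e.g., 12 weeks of parent training and adolescent CBT") and otherwise fixes 12 sessions, so L is varied: 84 days (12 weeks), and 98 and 112 days (14 and 16 weeks, assumed).

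| L (days) | d = 0 | d = 28 | d = 56 | d = 84 |
|---|---|---|---|---|
| 84 | 0 | 19.4 | 47.4 | 75.4 |
| 98 | 5.4 | 33.4 | 61.4 | 89.4 |
| 112 | 19.4 | 47.4 | 75.4 | 90.0 |

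In the last cell the course ends on day 84 + 112 = 196, so the visit on day 182.6 comes before the end of treatment.

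**4. The same quantity under a treatment-start anchor.** Recall days inside the course = max(0, L − 92.6), which is 0, 5.4 and 19.4 days for L = 84, 98 and 112, whatever the delay. That anchor avoids overlap only if the course ends within about 92 days of starting. In PT/ACBT+MED, recall may cover ongoing medication under either anchor, because medication visits continue throughout participation.

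**The case against.** The strongest reply is that the two sections can be read together. Follow-up Assessment and Interventions calls all three arms treatment conditions just before it mentions a start date, so the start may mean entry to the assigned condition. The other section already gives every randomised teen a date. On that reading only a difference in wording remains. The reading is possible, but no entry date is defined for monitoring, and the other section would still name a different anchor.

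Second, the harm is hypothetical. It needs the treatment-start rule to be followed, a real delay, and monitoring timed from randomisation. The documents establish none of these, and nothing in them supports a lag as long as 12 weeks. This stands in full. A shifted window is not in itself bias, and if monitoring were given a start date with the same delay there would be no shift.

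Third, the medication is described as concurrent with PT/ACBT, and the prior consultation affects only teens already medicated. This narrows the ambiguity between first session and first dose without removing it.

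Fourth, a visit labelled post-treatment sits more naturally on a treatment-start clock, and an assigned start date for monitoring would also align the arms. That would work, but it needs a new date for monitoring and for teens who never start. Randomisation is the only candidate date the documents already define for all three arms.

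**Conclusion.** The conflict is real: two current sections give different anchors for the same visit, and one of those anchors is undefined for the control arm. Confidence is high on that textual point only. The documents show no actual timing difference between arms. The consequence depends on an unreported delay and on how monitoring visits were scheduled. Under the conditions stated above, the shift equals the delay day for day, and it is nil if the delay is nil. The point should be corrected because it concerns the only randomised comparison and the correction is cheap. It does not by itself invalidate the comparison.

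**What to change.** Reconcile the two sections by changing the sentence in Follow-up Assessment and Interventions, for example:

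> *The post-treatment visit is due 6 months after the date of randomization in all three conditions, regardless of whether the assigned treatment has begun.*

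The one-year visit then falls 18 months after randomisation in every arm. In addition:

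- State one visit window, the same for all arms. A common anchor without a window does not ensure comparable timing.
- Record the treatment start and end dates for each treated teen.
- Report actual months since randomisation by arm at both visits, including any visits already made on the other anchor.

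The cost is one sentence, a scheduling rule with a window, two dates per treated teen and one descriptive table. If visits have already been made on the treatment-start clock, the data will mix anchors, and the table will show by how much. The trade-off is the overlap in step 3 of the working: late starters will report some days that fall inside PT/ACBT. With a long delay and a long course, the visit may precede the end of treatment. The recorded dates allow this to be described.
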